2.1 Objectives & Hypotheses

Objective:

To compare rates of etonogestrel implant discontinuation in implant initiators who are given advance provision of combined oral contraceptive pills (COCs) and a bleeding rescue regimen (COCR intervention) to participants given standard counseling (comparator).

Secondary Objectives:

1. To determine if participants initiating the contraceptive implant who are also provided COCR are more likely than participants receiving standard counseling to:
 - a. report higher levels of satisfaction with their contraceptive implant at one year following initiation
 - b. require less clinical follow-up and clinical resources in the year following initiation.
2. To determine if people who did not enroll in this randomized controlled trial are similar in characteristics and outcomes to the enrolled group and specifically compared to the “usual care” arm.

Primary Hypothesis: We hypothesize that participants who initiate the contraceptive implant and are given advance provision of COCR will be significantly less likely to discontinue their implant in the year following insertion than those given standard counseling

Secondary Hypothesis: We hypothesize that participants who initiate the contraceptive implant and receive the COCR intervention will:

- a. be more satisfied with their contraceptive implant
- b. make and attend fewer follow-up visits in the year after initiation.

2.2 Background & Rationale, Significance of Selected Topic & Preliminary Data

The contraceptive implant is a highly effective and safe contraceptive method for adolescents. Although usually well tolerated, the most common reason for early discontinuation is bleeding. The contraceptive choice study looked at LARC continuation in adolescents (under 20yo) and found that 80% of adolescent continued at 1 year and 50.8% of adolescents continued the implant at 3 years. Despite this, adolescents who do discontinue often report bleeding as the reason (Cohen 2019). Those who get the implant removed often switch to a less effective method.

Studies of interventions for bleeding in implant users have been small, brief and have rarely evaluated long term bleeding outcomes, long term continuation or satisfaction.

In a 2015 study by Guiahi et al, 32 women with self-reported bothersome bleeding and current bleeding episode of at least 7 consecutive days were randomized to COC or placebo for 14 days. They found an increased likelihood of cessation of bleeding with COCs but bleeding often resumed within a week of discontinuation. They did not look at participant satisfaction or continuation of their method. Hou et al (2016) also conducted a randomized placebo-controlled trial of bleeding with 26 participants. Most women in both arms reported bleeding improvement at 4 weeks, although those on COCs were significantly more likely to improve. They followed participants for 2 months after a 4-week treatment trial. Of 13 COC users, 8 opted to continue study treatment after the 4 weeks. Four of the 26 participants requested implant removal by 3 months. 3 of these women had used COCs at some time during the study.

	
Chen et al (2018) studied concurrent use of implant and COC in a proof of concept study. Two of 19 participants had the implant removed at 6 month follow up but neither requested removal for bleeding complaints. There were no adverse events and use of COCs and implant was well tolerated.
 
These studies have identified that COCs may be an effective intervention for reported bothersome bleeding during implant use and are safe to use in conjunction with the implant. Whether offering a COC intervention increases satisfaction or continuation of the implant remains unexplored.
 
Studies evaluating other interventions for breakthrough bleeding on the contraceptive implant have had mixed results. Mifepristone, a selective progesterone receptor modulator, is reported to up regulate endometrial estrogen receptors to induce proliferation and reduce vaginal bleeding. A study on the levonorgestrel implant (Cheng 2000) showed some improvement in episodes of unscheduled bleeding but a pilot study in etonogestrel implant users did not show clinical benefit (Weisberg 2006)
 
Nonsteroidal anti-inflammatory drugs (NSAIDs) have been used to treat irregular bleeding and showed some decrease in bleeding episodes when taking three times a day for 5 days (Phaliwong P, 2004). Appropriate medication, dose and regimen have not been established.
 
Other treatments including mifepristone plus estrogen or doxycycline (Weisberg E 2006), tamoxifen (Simmons 2017) and ulipristal acetate (Zigler 2018) have all been shown to have some benefit. Challenges have been found with all studies in improving bleeding patterns long term after intervention has been discontinued.
 
COC's have been recommended in expert opinion as a first-choice medication to control persistent bleeding due to low cost and the most supporting evidence for short term benefit (Mansour 2011).
 
Hou, et al reported that women who initially requested removal of the implant were more likely to continue to desire removal at study conclusion. It is possible that by the time participants have come to clinic for bothersome bleeding they are less willing to try an intervention or be satisfied with its outcomes. If an intervention for bleeding was provided at implant insertion to be used as needed, this could give a participant a plan for addressing this possible side effect and a sense of control over their bleeding patterns.

2.3 Study Design	
This is a randomized controlled open-label clinical intervention trial. Participants will be recruited from the Children's Hospital Colorado BC4U clinic. This clinic is a Title X supported family planning clinic that offers free, confidential, same-day contraception to patients aged younger than 25 years. Participants will be eligible if they are 14-23.9 years old and are new starters of the etonogestrel implant. Exclusion criteria will be any contraindications to estrogen-containing birth control, and plans to move from the area (where it would not be reasonable to come to the clinic) in the next 12 months. All patients seeking contraception in our clinic undergo thorough evaluation (personal and familial health history) for contraindications to any forms of contraception that are offered as part of the contraceptive assessment and counseling process. For participants under 18 years of age, we will obtain a waiver of parental consent from the IRB. This is available because reproductive services

	
are confidential for all adolescents in the state of Colorado, and the University of Colorado IRB recognizes that requiring parental consent for studies which involve the same risks as routine contraceptive care is discriminatory against adolescent participation. Patients who agree to participate will be randomized to the advance provision intervention (COCR) or to standard care (SC). Standard of care in our clinic is to tell all participants initiating the implant to call or follow-up if they have undesired side-effects. If they present with a complaint that is bleeding-related, they are told over the phone or in person that they have the option to try COCs for bleeding management. Those who desire COCs as an intervention are prescribed (over the phone) or given (in person) 3 packs of COCs. They are told to take one pill per day until the first pack is complete and save the remaining 2 packs for possible future use. Participants in the SC arm will be offered care according to our standardized protocol, which may include STI testing, reassurance and monitoring, prescription of COCs if desired, or removal. Participants in the COCR arm will receive three packs of combined oral contraceptive pills (35mcg ethinyl estradiol/norgestimate) and a specific protocol for their use for bothersome bleeding, as described below. We chose ethinyl estradiol/norgestimate because it is the main oral contraceptive pill that is provided in the family planning clinic through Title X governmental grant funding. Because we do not normally provide patients with pills at the time of implant insertion, Merck will cover the additional cost to the clinic for purchasing these pills. Participants in this arm may receive additional COCs as needed. Participants who receive COC's in any arm will be made aware of possible side effects of COC's including breast tenderness, headaches nausea, and bloating. Less common side effects could be related to mood or reduction in sexual libido. They will also be counseled on rare but more dangerous cardiovascular effects of combined contraceptive pills which increase increased blood pressure, venous thromboembolism and myocardial infarction or stroke. These risks are very low with the absolute risk of VTE in young women approximately 0.06 per 100 pill years (Solymoss S 2011). The risk of stroke in adolescents on combined oral contraceptive pills is 3.4 per 100,000 woman-years (Lidegaard 2012). The risks of VTE, MI and stroke in young woman on the pill are significantly lower than during pregnancy or the postpartum period.
 
There is no clear recommendation for routine follow up visits after initiating combined hormonal contraceptives (USSPRCU Curtis KM 2016) but standard of care in the family planning clinic is to require a visit annually to monitor weight and blood pressure in order to continue use.
 
All participants will be followed-up at 3 months, 6 months and one year by phone and/or online survey per participant preference. We will assess self-reported bleeding pattern, other side-effects, and overall satisfaction with the implant and with bleeding patterns. We will query the electronic medical record (Epic, Verona Wisconsin) to capture phone calls to clinic regarding the implant, appointments made related to the implant, and follow-up appointments attended. We will also assess use of COCs, implant discontinuation, and post-implant contraceptive method.
 
We will also perform a similar medical record review to include people attending the clinic in the same time frame as the randomized trial who met inclusion criteria but were not enrolled in the study. This portion would be medical record review only and not include any contact with any patients.

2.4 Study Flowchart	Please see study flowchart in section 2.5.
2.5 Study Procedures	This is an open-label randomized controlled trial. Participants will be recruited from the adolescent family planning clinic (BC4U) if they are new initiators of the

contraceptive implant. Participants will be eligible if they are 14-23.9 years old. Exclusion criteria will be any contraindications to estrogen containing birth control. We will obtain a waiver of parental consent as reproductive services are confidential in all adolescents in the state of Colorado.

We will use a pragmatic study design. When an order is placed in the EMR system (Epic), a message is generated to the provider to ask the patient about interest in participation, to review study procedures and inclusion and exclusion criteria. If the patient qualifies, the consent/assent document is generated, and the provider is asked to review and have the patient sign if she desires. All providers are HIPAA and GCP-certified. Participants will be automatically randomized by the EMR after consent, and study documents and instructions appropriate to the randomization group will be generated. We will use similar methods as those described in Curtis et al. This pragmatic study design is already in use in several protocols at University of Colorado Hospital. Providers will do all counseling for participants in either group. Participants in the COCR group will receive 3 packages of COC pills. They will be instructed to use the pills if their bleeding is bothersome AND it lasts more than 5 days. At day 6 of bleeding they should start the pills and take them daily until they finish the pack (21 active pills). If bleeding continues and is bothersome, they may begin the next pack of active pills. If bleeding stops, but then resumes at any time in the course of the study period and is bothersome to them they should start another pack. They can continue this throughout the time of their implant. They will be given refills on COC pills as needed. They may call and/or come into the clinic for follow up as desired. This information will be provided to the participants graphically, and at a 5th grade reading level.

Participants in the SC group will be counseled as usual on possible bleeding patterns with the implant. They will be told to call or follow up for any concerns with the implant, including bothersome bleeding. They will receive our clinic handout about the contraceptive implant.

We will obtain best and alternate phone numbers and email addresses. Each participant will be contacted by [name], [name], or the professional research assistant within 7 days of enrollment to confirm she has received any study supplies and understands her instructions.

Participants will be informed that we will contact them at 3, 6, and 12 months. At that time, we will offer a phone or online survey. We will make multiple attempts to contact them. We will also query the EMR for telephone calls and follow up appointments.

Participants will receive a \$25 gift card for initial study participation and a \$25 gift card for each follow up survey completed.

[figure not shown]
Participants from either group who would like their implant removed can come into clinic for removal. A standardized template will be used to document reason(s) for removal.

In the below flow diagram, all numbers are estimates based on our site's published and recent experience in patient volume, study participation, and follow-up rates.

We will also perform an identical medical records review for people who were not enrolled in the randomized trial (highlighted in the red box in the study flow diagram below) and will extract the variables highlighted in red below in the outcomes table. No other information will be examined for these patients.

We hypothesize that patients who are enrolled in the randomized trial and thus contacted by clinic staff after implant placement, are more likely to schedule follow-up visits to discuss bothersome bleeding patterns and less likely to have etonogestrel implant removed. The primary outcome for this secondary aim will be the number of appointments for breakthrough bleeding and implant removal.

Figure 1. Study flow diagram

2.6 Study Duration

We plan to enroll and randomize a total of 600 participants over a period of 12 months. We will follow all participants for up to 12 months post insertion. After completion of all study follow-up medical record review and data cleaning will take approximately three months.

2.7 Statistical Analysis and Sample Size Justification

[name] (Co-Investigator) will be responsible for analyzing the study data. This study is a non-blinded randomized controlled trial. Because this study involves standard clinical care, study arm will be identified in the electronic medical record and will be known to investigators and providers. However, no data will be aggregated or analyzed until study completion.

Variables:

The primary outcome variable will be retention of the contraceptive implant at 12 months post-insertion. Discontinuation will be determined through participant report at the 3, 6, and 12 month follow-up and by review of medical records.

Secondary outcome variables include:

Variable	Assessed by:
Satisfaction with bleeding profile	Likert scale ("very satisfied", "somewhat satisfied" and "not satisfied")
Satisfaction with method overall	Likert scale ("very satisfied", "somewhat satisfied" and "not satisfied")
Likelihood of recommending implant to a friend	Likert scale ("very likely," "somewhat likely" "not at all likely")
Follow up related to implant (visits or phone calls)	EMR review
Side effects attributed to implant	Phone/online survey

Additional variables include:

Variable	Assessed by:
Age	EMR
Race/Ethnicity	EMR
BMI	EMR

Statistical Methods

We will use standard bivariate statistics including Student's t-tests and non-parametric medians tests to compare continuous variables. We will use Chi-squared and Fisher's exact tests to compare dichotomous and categorical variables. The primary outcome will be analyzed using the Chi-squared test to generate an odds ratio and confidence intervals for continuation by study arm. Backwards stepwise logistic regression will be performed to identify independent predictors of implant discontinuation. In the first step, demographic variables will be included if they have a significant bivariate relationship to the outcome ($p < 0.1$). In the second step, each reproductive characteristic will be considered as a candidate predictor and included if it significantly ($p < 0.1$) improves upon the fit of the model from the first step. Study arm will be included in the third, final step. We will also compute estimates of time to discontinuation using Cox regression models.

Multiplicity

If necessary, we will use the Bonferroni method to correct for multiple comparisons.

Power/Sample Size:

Over the last 10 years BC4U clinic has placed approximately 1,200 implants per year. We anticipate that we will be able to enroll a total of 600 of the 1200 implant initiators (50%). Participants will be randomized in a 1:1 ratio. Thus, we will

	randomize 300 participants to each arm. Based on prior studies in this clinic (Richards 2017, Cohen 2017, Cohen 2019, Green 2019) , we hypothesize that 25% of participants in the SC arm will discontinue the implant within 12 months and 15% of participants in the COCR group will. With a loss-to-follow-up rate of 17% (from prior studies), we will have 80% power to detect this 10 percentage-point difference with a two-sided alpha of 0.05.
2.8 Specific Drug Supply Requirements	Nexplanons for this study will be purchased by BC4U clinic of Children's Hospital Colorado under the 340B program as per clinical standard of care. COCs for this study will be purchased by the BC4U clinic of Children's Hospital Colorado under the 340B program as per clinical standard of care. No drugs will be supplied by MSD.
2.9 Adverse Experience Reporting	We will use the Model Study Agreement reporting requirements for adverse events.
2.10 Itemized Study Budget	A preliminary study budget must be provided with the initial proposal submitted to give guidance to the MISP Review Committee as to the expected study costs. A refined itemized budget detailing the costs associated with the study should be provided with the final protocol or included in the study agreement as Exhibit B.

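### Implant-related contacts are identified in records that show the study arm, with no rule for COC refill contacts, so the same need may be counted differently in the two arms

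*Combined protocol and SAP*

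**What the plan says.** Secondary hypothesis b (section 2.1) is that COCR participants will "make and attend fewer follow-up visits in the year after initiation". The matching variable in the 2.7 table of secondary outcomes is "Follow up related to implant (visits or phone calls"), assessed by EMR review. Section 2.3 describes the source as a query of the record "to capture phone calls to clinic regarding the implant, appointments made related to the implant, and follow-up appointments attended".

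On blinding, 2.7 states that "study arm will be identified in the electronic medical record and will be known to investigators and providers". The one safeguard it offers is that "no data will be aggregated or analyzed until study completion".

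The arms reach COCs by different routes. For SC, section 2.3 makes COCs available on complaint: "If they present with a complaint that is bleeding-related, they are told over the phone or in person that they have the option to try" them. Those who want them are prescribed or given three packs, use one and keep two. COCR participants receive three packs at insertion, and section 2.5 adds: "They will be given refills on COC pills as needed".

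No section defines when a contact is related to the implant, says whether a COC refill contact counts, names who classifies contacts, or describes masked or duplicate classification. Section 2.5 promises an identical record review for eligible patients who did not enrol.

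**The concern.** Two features combine. First, deciding whether a contact is related to the implant takes judgement wherever the reason for the contact is ambiguous, and whoever decides can see the arm. Postponing aggregation and analysis until the end does not change that, because classification happens before analysis and from the same arm-labelled record.

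Second, the ambiguous contacts are not spread alike over the arms. An SC participant who wants pills for bleeding must first present with a bleeding complaint, which reads naturally as being about the implant. A COCR participant with the same need already has pills, so her later contact may be charted simply as a request for more. Nothing in the plan says whether that counts.

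At stake is objective 1b, which concerns clinical follow-up and clinical resources. A refill contact uses those resources whichever label it carries. If it is counted in one arm and missed in the other, the comparison measures charting as well as need. The undefined rule also carries over to the comparison with non-enrolled patients, whose main outcome is a count of appointments.

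**Working it through.** **The plan's own figure.** The documents give no contact rate, refill share or power for this outcome. The only power figure is for the primary outcome: 25% against 15% discontinuation, 300 per arm, 17% loss, two-sided alpha 0.05. Evaluable per arm: 300 × 0.83 = 249. With the pooled proportion 0.20, the null standard error is √(2 × 0.20 × 0.80 / 249) = 0.0358. The alternative standard error is √((0.25 × 0.75 + 0.15 × 0.85) / 249) = 0.0356. Power = Φ((0.10 − 1.96 × 0.0358) / 0.0356) ≈ 79.8%, against 80% stated. Contact counts do not enter it.

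**Illustration for the contact outcome.** Inputs:
- n = 300 per arm, from 2.7. No loss is applied, because the source is the record.
- True mean contacts per participant, m, equal in both arms. Assumed: 0.3 to 1.0.
- Share f of COCR contacts not counted, with all SC contacts counted. Assumed: 5%, 10% or 20%.
- Counts either Poisson (variance = mean) or overdispersed (negative binomial with k = 1, variance = mean + mean²).

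The apparent rate ratio is 1 − f. With V(x) the variance at mean x:

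z = m·f / √((V(m) + V(m(1 − f))) / n)

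Two-sided rejection rate = Φ(z − 1.96) + Φ(−z − 1.96)

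Worked case, m = 1 and f = 10%:
- Poisson: z = 0.10 / √((1 + 0.9) / 300) = 0.10 / 0.0796 = 1.257, giving 24%.
- Overdispersed: z = 0.10 / √((2 + 1.71) / 300) = 0.10 / 0.1112 = 0.899, giving 15%.

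| f | m = 0.3 (overdispersed to Poisson) | m = 0.5 | m = 1.0 |
|---|---|---|---|
| 5% | 6.0–6.3% | 6.5–7.2% | 7.3–9.5% |
| 10% | 9.3–10.6% | 11–14% | 15–24% |
| 20% | 24–29% | 33–45% | 46–73% |

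With f = 0 the rate is 5%. Simulation agrees to within sampling error. At f = 10% and m = 1, separate runs gave 15–16% (overdispersed) and 24–26% (Poisson).

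**The reverse case.** By symmetry, if the same share of SC contacts were lost and every COCR contact were counted, the rates would be the same, but COCR would appear to need more contacts.

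**What the shares mean.** At m = 1 there are 300 contacts per arm, so f = 10% is 30 uncounted contacts and f = 20% is 60. At m = 0.3 there are 90 contacts, and f = 10% is 9.

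**The case against.** A reader might infer that the bias must favour COCR. The documents do not support this. Under 2.5, COCR pills are supplied only for bothersome bleeding on the implant, so someone who sees the arm label has reason to count a COCR refill as implant-related, perhaps more readily than in SC. SC participants who start COCs also receive three packs and may later ask for more, so the clear contrast lies in the first SC request. The asymmetry is one of degree. These points stand.

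A reader might also infer that the damage would be permanent. It would not: the record is stored, 2.6 places record review after follow-up, and contacts can be extracted again under another rule. What would be lost is the credibility of a rule chosen after arm-visible classification.

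The size is open to challenge as well. Sixty uncounted refill contacts among 300 participants, each of whom starts with three packs, is a number no section supports. The test matters too. Section 2.7 allows a medians test, and a run with one form of it (Mood's test) at m = 1 and f = 10% rejected 9–16% of the time. Finally, 2.3 and 2.5 speak of querying the record, so contact-by-contact judgement is partly an inference. However, 2.7 calls it EMR review, and a query also needs a rule for what is related to the implant. None is given.

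**Conclusion.** The point holds as a weakness in the measurement of one family of secondary outcomes. As written, the plan leaves hypothesis b open to classification that depends on arm: the arm is visible, the criterion is undefined, and the contacts most in doubt arise by different routes in the two arms. If COCR refill contacts were left out, COCR would appear to need fewer contacts. If they were counted more readily than the equivalent SC contacts, the error would run the other way. The documents settle neither direction nor size.

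The false-positive rates illustrate sensitivity and do not predict a result. They rest on assumed contact rates, an assumed one-sided loss and a normal approximation. Within those assumptions, a 5% loss does modest harm (about 6–10%). A 10% loss can double the nominal rate or worse (about 9–11% at 0.3 contacts per participant, 15–24% at 1.0). Implant retention at 12 months and its sample size are unaffected. The change should be made because it is cheap and can be settled before any contact is classified.

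**What to change.** In 2.7:

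1. Define the outcome as any participant-initiated visit or call about the implant, bleeding or COCs, including refills and COC orders, by the same rule in both arms. Exclude study-initiated calls: the contact within 7 days of enrolment and the 3-, 6- and 12-month surveys.
2. State whether hypothesis b is tested on visits, calls or both. Section 2.1 names visits only, while the 2.7 variable adds calls.
3. Extract contacts for all participants in one query on coded encounter reason, diagnosis or order, without the arm field. Freeze the contact file, then merge arm.
4. Apply the same rule to the review of non-enrolled patients.
5. Report all-cause clinic contacts as a sensitivity analysis, since that count needs no judgement of relatedness.

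The cost is SAP wording and one query, with no change to treatment, enrolment or follow-up. Some differential capture may remain, because codes and orders are entered by providers who know the arm and some contacts exist only as free text. Counting implant, bleeding and COC contacts together removes much of the dependence on which label was used, and the all-cause count helps to check the rest, although unrelated contacts will dilute it.

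### The only listed side-effect outcome is limited to effects attributed to the implant, so the arm comparison may miss side effects of the COCs under test

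*Combined protocol and SAP*

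**What the plan says.** Section 2.7 (Variables) gives five secondary outcome variables. The only one on side effects is "Side effects attributed to implant", assessed by phone or online survey. The survey wording, the person who makes the attribution and any analysis of harms by arm are not given.

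Section 2.3 describes the 3-, 6- and 12-month follow-up of all participants more broadly: "We will assess self-reported bleeding pattern, other side-effects, and overall satisfaction with the implant and with bleeding patterns". It sets no attribution limit. It also plans to measure exposure: "We will also assess use of COCs, implant discontinuation, and post-implant contraceptive method".

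The same section says that participants who receive COCs, in either arm, "will be made aware of possible side effects of COC's including breast tenderness, headaches nausea, and bloating", and it adds mood and libido effects as less common. These effects appear as counselling content only and are not listed as outcomes.

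Section 2.9 deals with adverse events in one sentence: "We will use the Model Study Agreement reporting requirements for adverse events". That agreement is not part of the documents.

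Section 2.7 also states: "This study is a non-blinded randomized controlled trial".

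**The concern.** The arms differ by design in the advance supply of COCs, so the side effects of most interest are those that COCs may cause. The listed outcome counts a symptom only if it is put down to the implant. This raises two problems.

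- A symptom caused by the pill and correctly attributed to it falls outside the outcome. A real COC effect can then be absent from the arm comparison.
- Attribution is a judgement that allocation can influence. Every COCR participant is handed pills at enrolment and told which symptoms they may cause. An SC participant reaches that position only after presenting with bleeding and choosing COCs. With equal symptom rates, fewer symptoms may be blamed on the implant in the COCR arm.

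At stake is what the trial can report about the tolerability of its own intervention in participants aged 14 to 23.9 years.

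**Working it through.** **The plan's own figure.** Section 2.7 plans 300 per arm with 17% loss to follow-up, so 300 × 0.83 = 249 per arm are analysed. For 25% against 15% and two-sided alpha 0.05:

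- SE under no difference = √(2 × 0.20 × 0.80 / 249) = 0.0358
- SE under the alternative = √((0.25 × 0.75 + 0.15 × 0.85) / 249) = 0.0356
- power = Φ((0.10 − 1.96 × 0.0358) / 0.0356) = 79.8%

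The stated 80% reproduces and does not depend on the side-effect item. The 249 per arm is carried into what follows.

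**Illustration 1: equal symptom rates, unequal blame.** None of these inputs is in the documents; all are assumed. A symptom occurs in 30% of each arm. A share u of each arm uses COCs, and a share a of symptomatic users blame the pill. The outcome then reads 0.30 × (1 − u × a) in each arm, and the false difference is 0.30 × a × (u in COCR − u in SC).

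| COC use, COCR vs SC | Share blaming pill | Outcome reads, COCR vs SC | False difference (points) | Trials significant at 249 per arm |
|---|---|---|---|---|
| any | 0 | 30% vs 30% | 0 | 5% (nominal) |
| 30% vs 10% | 1/3 | 27.0% vs 29.0% | 2.0 | about 8% |
| 40% vs 20% | 1/2 | 24.0% vs 27.0% | 3.0 | about 12% |
| 50% vs 20% | 1/2 | 22.5% vs 27.0% | 4.5 | about 21% |
| 50% vs 10% | 1/2 | 22.5% vs 28.5% | 6.0 | about 34% |

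The last column uses the same power formula as above, with both tails counted.

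In an extreme case, one third of all symptomatic COCR participants blame the pill and no SC participant does. The outcome then reads 0.30 × 2/3 = 20% against 30%. With SEs of 0.0388 and 0.0385, the share of significant trials is Φ((0.10 − 1.96 × 0.0388) / 0.0385), about 73%. This is hard to reach under section 2.5, where pills are started only for bothersome bleeding lasting more than 5 days. If two thirds of the COCR arm used pills, half of symptomatic users would have to blame them, with no such attribution in SC.

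**Illustration 2: a true COC effect.** Again by assumption, 30% in each arm have a side effect blamed on the implant, COC use is 50% vs 20% or 30% vs 10%, and COCs cause a side effect in 10% to 20% of users. The true all-cause difference is 0.70 × (COC effect rate) × (difference in use):

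- smallest: 0.70 × 0.10 × 0.20 = 1.4 points against COCR
- largest: 0.70 × 0.20 × 0.30 = 4.2 points against COCR

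The implant-attributed item shows none of this if no COC effect is blamed on the implant, half if half are, and all of it if all are.

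**Rare harms.** At the protocol's VTE rate of 0.06 per 100 pill-years, 300 pill-years would yield 300 × 0.06 / 100 = 0.18 expected events. No wording of the item would let the trial compare arms on these. The point concerns common effects.

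**The case against.** The strongest reply is that the documents do not confine data collection to implant-attributed effects. Section 2.3 plans to ask about other side effects without restriction and to assess COC use, and section 2.9 adopts an adverse event procedure. A reader might infer from the table row that side effects are recorded only when the participant blames the implant, or that the trial cannot report the harms of COCs. Neither inference is supported. The survey wording is not shown, the agreement behind section 2.9 is not reproduced, and the documents do not say who attributes or whether attribution limits collection or is coded afterwards. What remains is that planned collection is not a listed outcome, and that the two sections disagree.

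A reader might also infer that the comparison is shown to be tilted toward COCR. It is not. SC participants who present with bleeding may also receive COCs ("prescription of COCs if desired, or removal") and the same side-effect counselling, so they too can blame the pill. COCR participants may blame pill effects on the implant, which would remove the bias. The direction is plausible, and its size may be nil.

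Finally, this is one of five secondary variables and belongs to no stated objective or hypothesis. That is correct and limits the weight of the point. It does not justify leaving the intervention's own common side effects without a listed outcome.

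**Conclusion.** The point holds as a fault in outcome definition with a possible bias, not a demonstrated one. The only side-effect outcome listed for analysis is restricted to the implant, conflicts with section 2.3, and leaves no COC or all-cause side-effect outcome in a trial whose randomised intervention is COCs. Followed as written, the table makes the comparison depend on a judgement that open-label allocation can affect.

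Assuming a 30% symptom rate in both arms, the false difference runs from 0 to about 6 points under the as-needed uptake scenarios examined, with up to about 34% of trials significant at 249 per arm. The 10-point result (about 73%) needs an extreme assumption and should not be read as the expected size. Symptom rates, COC uptake and blame shares are all assumed, and the documents supply none of them. Implant retention at 12 months, its analysis and the sample size are unaffected.

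**What to change.** Change the row in the section 2.7 table to all side effects regardless of attributed cause. Ask it with the same item in both arms at 3, 6 and 12 months, and include as listed symptoms the COC effects that section 2.3 already names. Record perceived cause (implant, COC, unsure) as a separate descriptive field. Compare arms as randomised on the all-cause item, and align the wording of sections 2.3 and 2.7.

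The cost is one table row, a reworded survey item and a slightly longer survey. Sample size and primary analysis do not change.
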